**Table 5. Analysis Intervals for AEs, SAEs, MAEs, NDCMCs, and Days Missing School or Work Because of AEs**

Interval #	Group	Analysis Interval	Analysis Population	Interval Start Date (Inclusive)	Interval Stop Date (Inclusive)	Safety Data
10	Groups 1, 2	6 Months after Vaccination 1	Vax 1 safety	Vax 1 date (Groups 1, 2)	6 Months after Vax 1 date	SAEs, MAEs, NDCMCs, days missing school or work because of AEs
11	Groups 1, 2	6 Months after Vaccination 2	Vax 2 safety	Vax 2 date (Groups 1, 2)	6 Months after Vax 2 date	SAEs, MAEs, NDCMCs, days missing school or work because of AEs

Abbreviations: MAE = medically attended adverse event; NDCMC = newly diagnosed chronic medical condition; Vax = vaccination.

Note: 183 Days will be used as the duration for programmatic determination of 6 months for Interval 11.

Three analysis intervals will be applied to immediate AEs (Table 6).

**Table 6. Analysis Intervals for Immediate AEs**

Interval #	Group	Analysis Interval	Analysis Population	Interval Start Date/Time (Inclusive)	Interval Stop Date/Time (Inclusive)
1	Groups 1, 2	Vaccination 1	Vax 1 safety	Vax 1 time	Vax 1 time + 30 minutes
2	Groups 1, 2	Vaccination 2	Vax 2 safety	Vax 2 time	Vax 2 time + 30 minutes
3	Group 2	Vaccination 3	Vax 3 safety	Vax 3 time	Vax 3 time + 30 minutes

Abbreviation: Vax = vaccination.

### **3.5.2. Pregnancy Testing**

The results of the urine pregnancy tests collected at Visits 1, 4, and 9 (Group 2 only) will be recorded.

### **3.5.3. Laboratory Data**

Laboratory assessments will not be collected for this study.

### **3.5.4. Medical Device Errors**

Medical device incidents or malfunctions of the device that result in an incident will be detected, documented, and reported during all periods of the study in which the medical device is used. If a medical device error involves an AE, it will be summarized according to AE reporting conventions.

## **3.6. Study Conduct**

### **3.6.1. Nonstudy Vaccines and Concomitant Medications**

The name and date of administration of any nonstudy vaccine (or allergen immunotherapy) given from the signing of the ICD up to approximately 6 months after Vaccinations 1 and 2, within approximately 1 month after Vaccination 3 (Group 2 only), and within 28 days before administration of study intervention at Visit 4 and Visit 9 will be recorded on the CRF. The name and date of administration for any nonstudy meningococcal vaccine received will be collected from the signing of the ICD up to the end of study participation.

Concomitant vaccines and medications permitted during the study include:

- Nonstudy vaccines used in the event of a disease outbreak or pandemic are allowed. In such situations, effort should be made to appropriately plan the administration of study intervention around dosing of the pandemic vaccine.
- Nonstudy vaccines (other than any meningococcal vaccines) that are part of recommended immunization schedules are allowed anytime during the study but should not be administered within 14 days (for nonlive vaccines) and 28 days (for live vaccines) before or after administration of study intervention.
- Antipyretic and other pain medication to treat symptoms following administration of study intervention is permitted.
- A local anesthetic may be used at the site of the blood draw.
- Topical antibiotics are permitted.
- Topical and inhaled corticosteroids are permitted.
- Hormonal contraceptives that meet the requirements of this study are allowed to be used in participants who are WOCBP.

The name, start and stop dates, and route of administration for concomitant medications (prescription and nonprescription) used to treat AEs from the signing of the ICD through the final visit will be recorded in the CRF.

Treatments will be categorized according to the current version (at the time of reporting) of the WHO Drug Dictionary.

#### 4. ANALYSIS SETS (POPULATIONS FOR ANALYSIS)

Data for all participants will be assessed to determine if participants meet the criteria for inclusion in each analysis population prior to unblinding and releasing the database and classifications will be documented per standard operating procedures.

Population	Description
Enrolled	All participants who sign the ICD.
Randomly assigned to study intervention (as-randomized), also termed intent-to-treat (ITT) population	All participants who are assigned a randomization number in the IRT system.
Evaluable	Defined according to post-Vaccination 1 evaluable and post-Vaccination 2 evaluable criteria.
Modified intent-to-treat (mITT)	Defined according to post-Vaccination 1 and post-Vaccination 2 criteria.
Safety	All randomized participants who receive at least 1 dose of the study intervention and have safety data reported after vaccination. Participants will be analyzed according to the vaccine they actually received.

Defined Population for Analysis	Description
Post-Vaccination 1 evaluable population	
 
1. All randomized participants.
 
2. Eligible throughout Visit 2.
 
3. Received the study intervention at Visit 1 as randomized.
 
4. Had blood drawn for assay testing within the required time frames at Month 0 (Visit 1; before Vaccination 1) and Month 1 (Visit 2; 1 month after the first vaccination: window 28-42 days).
 
5. Had at least 1 valid and determinate MenA/C/W/Y assay result at Visit 2.
 
6. Had received no prohibited vaccines or treatment through Visit 2.
 
7. Had no important protocol deviations through Visit 2.
 

Post-Vaccination 2 evaluable population	
 
1. All randomized participants.
 
2. Eligible throughout 1 month after the second dose of MenABCWY.
 
3. Received the study intervention at Visit 1 (for Groups 1 and 2) and Visit 4 (for Group 1) and Visit 9 (for Group 2) as randomized.
 
4. Had blood drawn for assay testing within the required time frames at Month 0 (Visit 1; before Vaccination 1) and at 1 month after the second MenABCWY vaccination (Visit 5 for Group 1 and Visit 10 for Group 2: window 28-42 days).
 

Defined Population for Analysis	Description
	
5. Had at least 1 valid and determinate MenA/C/W/Y or MenB assay result at 1 month after the second MenABCWY vaccination (Visit 5 for Group 1 and Visit 10 for Group 2).
 
6. Had received no prohibited vaccines or treatment through Visit 5 (Group 1) or Visit 10 (Group 2).
 
7. Had no important protocol deviations through Visit 5 (Group 1) or Visit 10 (Group 2).

Post-Vaccination 1 mITT population	All participants who received at least 1 study vaccination and had at least 1 valid and determinate MenB or MenA/C/W/Y assay result available at any time point from Visit 1 to Visit 2.
Post-Vaccination 2 mITT population	All participants who received at least 1 study vaccination and had at least 1 valid and determinate MenB or MenA/C/W/Y assay result available at any time point from Visit 1 to Visit 5 for Group 1 and from Visit 1 to Visit 10 for Group 2.
Vaccination 1 safety population	This population will include participants who received the first dose of study intervention at Visit 1 and for whom safety information from Visit 1 up to Visit 4 is available in Groups 1 and 2.
Vaccination 2 safety population	This population will include participants who received the second dose of study intervention at Visit 4 (MenABCWY for Group 1, saline for Group 2) and for whom safety information from Visit 4 up to Visit 7 (for Group 1) or Visit 9 (for Group 2) is available.
Vaccination 3 safety population	This population will include participants who received the third dose of study intervention at Visit 9 (MenABCWY for Group 2) and for whom safety information from Visit 9 through Visit 10 is available.
Follow-up safety population 1	This population will include participants who received the first dose of study intervention and for whom safety information from Visit 2 up to Visit 4 in Groups 1 and 2 is available.
Follow-up safety population 2	This population will include participants who received the second dose of study intervention (MenABCWY for Group 1, saline for Group 2) and for whom safety information from Visit 5 up to Visit 7 (for Group 1) or Visit 9 (for Group 2) is available.

For determination of the evaluable population(s), items 1 through 5 will be computerized checks of the data, while items 6 and 7 will be determined by clinical review. An important protocol deviation is a protocol deviation that, in the opinion of the sponsor's global medical monitor, would materially affect assessment of immunogenicity, eg, participant receipt of a prohibited vaccine or medication that might affect immune response or a medication error with suspected decrease in potency of the vaccine. The global medical monitor from the sponsor will identify those participants with a protocol deviation prior to unblinding of the study.

For participants withdrawn early, they will be included in the respective follow-up population, in case they have any type of AEs in the respective AE follow-up intervals.

For Analysis 1 (per [Section 7.1](#)), the post-Vaccination 1 evaluable population will be fully defined for both Groups 1 and 2. Similarly, the post-Vaccination 2 evaluable population will be fully defined for Group 1 for Analysis 1. The final determination of the protocol

deviations, and hence the post-Vaccination 2 evaluable population for Group 2, will be completed for the final analysis.

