6.1. Study Intervention(s) Administered

MenACWY-TT, supplied as a single-dose vial containing lyophilized powder, will be reconstituted with bivalent rLP2086 supplied as a high-fill volume PFS, as detailed in the IP manual, and 0.5 mL of the resultant MenABCWY will be administered via intramuscular injection. The final MenABCWY composition includes rLP2086 subfamily A and B proteins formulated at 120 $\mu\text{g}/\text{mL}$ /subfamily, purified capsular polysaccharides of

N meningitidis serogroups A, C, W, and Y at a concentration of 10 µg/mL/polysaccharide type conjugated to tetanus toxoid [REDACTED], in [REDACTED] histidine [REDACTED] sodium chloride, 0.5 mg/mL aluminum as AlPO₄, 0.035 mg/mL polysorbate 80, and [REDACTED] sucrose.

The placebo is sterile normal saline solution for injection and will be administered as a 0.5-mL intramuscular injection.

Intervention Name	MenABCWY	Placebo (Normal Saline)
Dose Formulation	MenACWY-TT will be reconstituted with bivalent rLP2086, supplied as a high-fill volume PFS	Sterile normal saline solution for injection
Dosage Level(s)	0.5-mL dose at Visits 1 and 4 (Group 1) or at Visits 1 and 9 (Group 2)	0.5-mL dose at Visit 4 (Group 2)
Route of Administration	Intramuscular	Intramuscular
IMP or NIMP	IMP	IMP
Sourcing	Pfizer	Pfizer
Packaging and Labeling	Each MenABCWY kit will consist of a vial of MenACWY-TT, bivalent rLP2086 high-fill volume PFS, and vial adaptor. Kits will be packaged in a carton and labeled as required per country requirement. Kits provided for Visits 1 and 4 will include a blinded label and a tamper evident seal. Kits provided for Visit 9 will include an open label and a tamper evident seal.	Study intervention will be provided in a single-dose PFS. Each syringe will be packaged in a carton and labeled as required per country requirement. Kits provided for Visit 4 will include a blinded label and a tamper evident seal.

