Post-Vaccination 2 evaluable	
All randomized participants who were:
 
 eligible throughout 1 month after the second dose of MenABCWY, received the investigational product at Visit 1 (for Groups 1 and 2) and Visit 4 (for Group 1) and Visit 9 (for Group 2) as randomized, had blood drawn for assay testing within the required time frames at Month 0 (Visit 1; before Vaccination 1) and at 1 month after the second MenABCWY vaccination (Visit 5 for Group 1 and Visit 10 for Group 2: window 28-42 days), had at least 1 valid and determinate MenA/C/W/Y or MenB assay result at 1 month after the second MenABCWY vaccination (Visit 5 for Group 1 and Visit 10 for Group 2), had received no prohibited vaccines or treatment through Visit 5 (Group 1) or Visit 10 (Group 2), and had no important protocol deviations through Visit 5 (Group 1) or Visit 10 (Group 2). 
An important protocol deviation is a protocol deviation that, in the opinion of the sponsor's global medical monitor, would materially affect assessment of immunogenicity (eg, participant's receipt of a prohibited vaccine or medication that might affect immune response or a medication error with suspected decrease in potency of the vaccine).

Post-Vaccination 1 mITT	All participants who received at least 1 study vaccination and had at least 1 valid and determinate MenB or MenA/C/W/Y assay result available at any time point from Visit 1 to Visit 2.
Post-Vaccination 2 mITT	All participants who received at least 1 study vaccination and had at least 1 valid and determinate MenB or MenA/C/W/Y assay result available at any time point from Visit 1 to Visit 5 for Group 1 and from Visit 1 to Visit 10 for Group 2.

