#### **4.1. Vaccine Misallocation**

- Vaccinated but not randomized: These participants will be included in the safety population for safety analysis and will be reported under the vaccine group based on the vaccine received, but will be excluded from immunogenicity analyses.
- Randomized but not vaccinated: These participants will be included in the ITT population and excluded from any safety analyses. They may be included in the mITT populations if any assay results are available and will be reported under their randomized group for immunogenicity analyses.
- Randomized but received incorrect vaccine: These participants will be included in the mITT population for immunogenicity analyses if data are available and will be reported under the vaccine group based on the randomized vaccine. These participants will also be included in the safety population for safety analysis and will be reported under the vaccine group based on the vaccine received.

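### The evaluable-set dosing check skips Visit 4 for Group 2: a MenABCWY dose given there in error is excluded from the primary analysis only by discretionary review, and from the 13-month ACWY analysis by nothing.

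*SAP*

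**What the plan says.** **Post-Vaccination 2 evaluable set.** Item 3 in SAP Section 4 names Visit 1 for both groups "and Visit 4 (for Group 1) and Visit 9 (for Group 2) as randomized". Protocol Section 9.3 has the same wording ("Visit 4 (for Group 1) and Visit 9 (for Group 2) as randomized"). Neither names Visit 4 for Group 2, although Protocol Section 6.1 and Table 1 assign Group 2 saline at that visit and Group 1 MenABCWY.

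**How the items are applied.** SAP Section 4 states that "items 1 through 5 will be computerized checks of the data, while items 6 and 7 will be determined by clinical review". Item 6 concerns prohibited vaccines or treatment and item 7 important protocol deviations. For Group 2 both run through Visit 10. A deviation is important if the sponsor's global medical monitor considers that it would materially affect the assessment of immunogenicity. One of the examples given is a "medication error with suspected decrease in potency of the vaccine".

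**Post-Vaccination 1 evaluable set.** Its dosing item is "Received the study intervention at Visit 1 as randomized". Its eligibility, blood-draw, assay, prohibited-treatment and deviation items all end at Visit 2 or earlier. Protocol Section 9.4.1 and SAP Section 6.3.1.2.1 use this set for the Group 2 ACWY percentage at or above LLOQ at 13 months after dose 1, which is measured at Visit 5.

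**Misallocation.** For participants who are randomized but receive the wrong vaccine, SAP Section 4.1 says: "These participants will be included in the mITT population for immunogenicity analyses if data are available". It does not say whether they leave the evaluable set.

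**The concern.** The two possible product errors at Visit 4 are treated differently. A Group 1 participant given saline fails a programmed check. A Group 2 participant given MenABCWY passes it and, if then dosed at Visit 9, reaches Visit 10 after three active doses instead of two. The error left to judgment is the one that would be expected to raise the Group 2 response.

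Two results are exposed. The first is the Group 2 result 1 month after the second dose: the primary MenB percentages and the supplementary comparisons of lower confidence limits with the thresholds in SAP Tables 9 and 10. The second is the exploratory Group 2 ACWY percentage at 13 months after one dose. That analysis is meant to describe how a single dose persists, and a participant boosted at Visit 4 gives no information on that.

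**Working it through.** **Step 1: trace a Group 2 participant given MenABCWY at Visits 1, 4 and 9 through the post-Vaccination 2 definition.**

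- Item 3: passes, because Visits 1 and 9 are as randomized and Visit 4 is not tested.
- Items 4 and 5: they refer to 1 month after the second MenABCWY vaccination but identify it as Visit 10 for Group 2. A program keyed to the visit passes the participant. One keyed to the count of active doses might not.
- Item 6: the prohibited list in Protocol Section 6.5.1 covers nonstudy meningococcal vaccines. A misallocated study dose is not on it.
- Item 7: reaches Visit 10 and can exclude the participant, by the medical monitor's judgment.

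**Step 2: trace a Group 2 participant given MenABCWY at Visits 1 and 4 through the post-Vaccination 1 definition.** Every item is settled by Visit 2, so nothing at Visit 4 can remove the participant. The Visit 5 titer, 1 month after a second dose, enters as 13 months after dose 1. No Visit 9 dose is needed for this to happen.

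**Step 3: reproduce the plan's own figures.** Protocol Section 9.2 has 150 per group and up to 20% excluded: 150 × 0.80 = 120. Clopper-Pearson half-widths at 72, 84, 96 and 108 of 120 are 9.09, 8.53, 7.51 and 5.77 points. Table 4 gives 9.1, 8.5, 7.5 and 5.8, so they agree. The gap in item 3 changes none of these.

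**Step 4: size of the bias.** Let m misdosed participants be kept among 120, all of them responders, and let the others respond at rate p. The observed rate is (1 − m/120)p + m/120, so

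bias = (m/120)(1 − p).

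The number m is not in the documents. Taking 1 to 3 as an assumption, the bias in percentage points is:

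| m | p = 90% | 80% | 70% | 60% |
|---|---|---|---|---|
| 1 | 0.08 | 0.17 | 0.25 | 0.33 |
| 2 | 0.17 | 0.33 | 0.50 | 0.67 |
| 3 | 0.25 | 0.50 | 0.75 | 1.00 |

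A single case as a check: 97/120 is 80.83% (lower limit 72.64%). Without the misdosed responder it is 96/119, or 80.67% (72.42%). The difference is 0.16 points in the percentage and 0.22 in the lower limit.

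The same formula applies to the 13-month ACWY percentage, with that set's own n. The documents give no expected rate at that time. If it were as low as 50%, then with n = 120 the bias for m = 1 to 3 would be 0.42 to 1.25 points.

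**Step 5: results near a threshold.** For each threshold, take the smallest count of 120 whose lower limit exceeds it, then remove m responders from numerator and denominator:

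| Threshold | Kept | Lower limit | Removed | Lower limit |
|---|---|---|---|---|
| 85% (A56) | 110/120 | 85.21% | 108/118 (m = 2) | 84.97% |
| 75% (A22, B44, each ACWY group) | 100/120 | 75.44% | 97/117 (m = 3) | 74.84% |
| 70% (composite) | 95/120 | 70.80% | 92/117 (m = 3) | 70.09% |
| 65% (B24) | 89/120 | 65.38% | 87/118 (m = 2) | 64.83% |

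Two or three errors can move a borderline result across the 85%, 75% or 65% threshold. Up to three do not move the composite across 70%.

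**The case against.** A reader might infer that a Group 2 participant given MenABCWY at Visit 4 is automatically analysed as a two-dose, 36-month recipient. The documents do not support that for the primary analysis. All seven items must be met, and item 7 covers Visit 4. Its test is any deviation that would materially affect the assessment of immunogenicity, and reduced potency is only an example. Protocol Section 8.3.10 counts giving an incorrect study intervention as a medication error to be recorded on the CRF. Protocol Section 6.3.3 has an unblinded clinician review unblinded deviations. The estimand describes participants who receive two doses and comply with key criteria, and naming only the mITT set in SAP Section 4.1 hints at exclusion from the evaluable set. Exclusion is therefore likely.

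The error should also be rare. Containers are assigned through the IRT, unblinded staff prepare and give the injections, and a participant not then dosed at Visit 9 fails item 3.

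These points stand for the post-Vaccination 2 set, including the 13-month MenB analysis, which uses it. They leave exclusion to judgment where the mirror error has a rule. None of them helps the 13-month ACWY analysis: item 7 of the post-Vaccination 1 set stops at Visit 2, and a missed Visit 9 dose is irrelevant there. That analysis is exploratory and confined to Group 2, which limits the consequence.

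Omitting Visit 4 for Group 2 may also have been deliberate, so that a missed saline injection excludes no one. That is a sensible aim and can be kept.

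**Conclusion.** The point holds in two parts. For the post-Vaccination 2 evaluable set, removing a Group 2 participant given MenABCWY at Visit 4 depends on discretionary review alone, while the opposite error in Group 1 is removed by program. For the Group 2 ACWY percentage at 13 months after dose 1, no rule removes the participant and the result is mislabelled.

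The effect is small. With 1 to 3 such errors among 120, all responding, it is about 0.08 to 1.0 points upward for true rates of 90% to 60%, against Table 4 half-widths of 5.8 to 9.1. It matters mainly for a Group 2 lower limit close to its threshold, taking the threshold assessment to use the evaluable set as the main analysis does. The number of errors and the response of every misdosed participant are assumptions. For the primary and threshold results, the range applies only if the item 7 review keeps them.

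Two larger readings are tempting but not supported. Counting each error as a full 1/120, so that three give 3/120 = 2.5 points, assumes that each participant would otherwise have been a non-responder left in the denominator; the remedy removes the participant from both counts. Nor does the gap bias a test between schedules. Protocol Section 9.1 and SAP Section 5.1 specify no hypotheses, and the threshold assessment is described as being without hypothesis testing.

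**What to change.** 1. In item 3 of the post-Vaccination 2 evaluable definition (SAP Section 4 and Protocol Section 9.3), require MenABCWY at Visits 1 and 4 for Group 1. For Group 2, require MenABCWY at Visits 1 and 9 and no MenABCWY at Visit 4. Do not require receipt of the saline injection, so that a missed saline dose excludes no one.
2. For the Group 2 ACWY analysis at 13 months after dose 1 (SAP Section 6.3.1.2.1 and Protocol Section 9.4.1), add the condition of no MenABCWY at Visit 4.
3. Optionally, extend the item 7 example to medication errors that add an active dose.

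The cost is one phrase per definition and a programmed check on administration data already recorded on the CRF. The planned 150 enrolled and 120 evaluable per group do not change.
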